## **LIST OF ABBREVIATIONS**

GCP	Good Clinical Practice
ISF	Investigator Site File
TMF/SMF	Trial/Study Master File
SOP	Standard Operating Procedure
CRF	Case Report Form
CNORIS	Clinical Negligence and Other Risks Scheme
PRP	Platelet Rich Plasma
DWG	Dorsal Wrist Ganglia/Ganglion
US	Ultrasound
PEM	Patient Evaluated Measure Score
DFML	[name] (Chief Investigator)
KH	Miss [name]
RN	Research Nurse
OR	Orthopaedic Registrar
SOS	Surgical Outcomes System
CM	Miss [name]

## **SUMMARY**

We propose to undertake a study where we examine the efficacy of Platelet Rich Plasma (PRP) to reduce recurrence in dorsal wrist ganglia (DWG). PRP is produced by centrifugation or spinning of a sample of the patient's blood, which separates out the different components. DWG are cystic collections arising from the wrist joint. Most common treatment is aspiration or reassurance as they have a high recurrence rate with any current treatment.

We will compare aspiration alone and aspiration with injection of PRP. We plan to recruit a maximum of 200 patients. We will assess the efficacy by contacting the patients by email or telephone at 6 weeks and 12 months. Adverse events will be screened for/ managed by a telephone call +/- review as necessary between 7 and 14 days. They will be asked to complete a questionnaire and a Patient Evaluated Measure score (PEMS).

## 1. INTRODUCTION

### 1.1. Background

Ganglia are soft tissue tumours which consist of a cavity with a collagen wall and filled with mucin rich in hyaluronic acid, glucosamine, globulin and albumin. The wall consists of collagen fibres arranged into sheets, with occasional mesenchymal cells. The lining is largely acellular with scattered fibroblasts. The cavity communicates with the joint. Although the aetiology is unclear, it is thought to arise from a rent in the capsule allowing escape of synovial fluid. 50% have underlying joint pathology on Arthroscopy.

The vast majority of ganglia present around the wrist, with 60-70% located on the dorsal aspect. The prevalence is men 25/100,000 and females 43/100000^5. MRI studies have shown that they are present in 51% of the asymptomatic population and 19% of patients presenting with wrist pain.

They are the second commonest referral to a hand surgeon. The most common reasons people present with their DWR are: cosmesis (38%), fear of malignancy 28%, pain 26% and 8% reduced function or sensation. Pain has been reported to be present in 89% of ganglia but only 19% felt it was significant. They are readily detectable by Ultrasound and MRI but the diagnosis is usually clinical.

Many solutions have been sought for dorsal wrist ganglia, but each has been troubled by recurrence. Non-surgical methods such as bursting it with firm pressure, simple aspiration +/- multiple puncture and aspiration plus steroid, hyaluronic acid or sclerosant all have similar rates of recurrence, but widely ranging between studies with rates from 18-93% reported and a 5% complication rate. Similarly surgical excision including the whole tract, which can be performed open or arthroscopically, is reported to have recurrence rates of 0-59% and up to 25% complication rate. When this is considered in the light that 49% of ganglia spontaneously resolve it is clear the solution has not yet been found.

Platelet rich plasma has been shown useful in many conditions and further studies are underway from bone, soft tissue and skin grafting, to tendinopathies, nerve injuries and even hair regrowth. It is defined as autologous plasma with a platelet count of 1,000,000 platelets/µl. It contains seven native growth factors plus cell adhesion molecules contained within a normal clot. Platelet function includes increasing cell mitosis, increasing collagen production, recruitment of inflammatory cells, initiating angiogenesis, and inducing cell differentiation.

Platelet rich plasma would be harvested from a sample of the patient's blood at the same visit as the aspiration and undergo the double centrifugation technique. Once activated the platelets secrete 70% of their stored growth factors in 10 minutes and the evacuation is almost complete after hour. They then synthesize additional factors until they die after about 8 days.

Autologous material is inherently safe and acceptable to patients. There is no risk of immune reaction or transmission of blood borne disease. It is never been associated with increased, or decreased, infection rates or induction of malignancy.

No prior studies on the use of PRP to prevent dorsal wrist ganglia recurrence have been found.

## **1.2. Rationale for Study**

We believe that by injecting platelet rich plasma into ganglia after aspiration of the contents, the platelets would be activated by exposure to the collagen wall and adherent clot would form in the cavity. It is plausible that the growth factors would cause differentiation of the mesenchymal cells within the walls and draw in inflammatory cells and thus from a relatively acellular position the means for healing have been provided. If the walls became scarred together obliterating the space then recurrence would be reduced. Aspiration is commonly performed and we do not believe any additional risk is posed to the patient from injection of PRP. Ganglia usually recur by 6 months so 1 year is adequate follow up.

**2. STUDY OBJECTIVES**

**2.1. Objectives**

**2.1.1. Primary Objective**

To assess if injection with Platelet Rich Plasma prevents recurrence after aspiration of dorsal wrist ganglia compared to aspiration alone?

**2.1.2. Secondary Objectives**

Does aspiration of dorsal wrist ganglia with or without injection of Platelet Rich Plasma alter PEM Score after 6 weeks and 12 months?

**2.2. OUTCOMES**

**2.2.1. Primary Outcome**

Presence or absence of ganglion recurrence as reported by the patient at 6 weeks and 12 months.

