**10. STATISTICS AND DATA ANALYSIS**

**10.1. Sample Size Calculation**

90 participants in each arm would give a 90% power to detect a change in recurrence rate of 25%. We believe this is adequate as current recurrence rates are 59%. This would need to be increased to 100 participants recruited per arm to allow for 10% drop out from follow-up.

As the recurrent rate is so large recruiting 90 patients would detect up to a 25% difference in recurrence rate. To ensure the trial is not extended beyond the point of answering our question we have also calculated numbers to allow for the trial to be closed early if we have sufficient data.

62 participants completing follow-up in each arm would give 90% power to detect a change in recurrence rate of 30%. This would need to be increased to 69 per arm to allow for 10% drop out from follow-up.

46 participants completing follow-up in each arm would give 90% power to detect a change in recurrence rate of 35%. This would need to be increased to 51 per arm to allow for 10% drop out from follow-up.

Therefore we will undertake initial data analysis after 51 and 69 participants have completed their 6 week review and if the difference in the recurrence rate is more than 35% or 30% then we will conclude the trial, but all outstanding follow up will be completed and data included in final analysis.

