**10.2. Proposed Analysis**

Statistical analysis will be performed to assess homogeneity of the study groups and efficacy of treatment. The primary outcome will use chi-squared test (with or without continuity correction). The secondary outcome will be assessed using independent T test if normally distributed or Mann-Whitney test if not.

The difference between the two groups will be significant if the p values are less than 0.05.

The analysis will be performed by [name] who is a Clinical Specialist on the Arthrex Research team based in Germany.

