**10.3. Missing Data**

Any patients with missing all follow up data will be deemed to have not completed follow up and will be excluded with a withdrawal form completed. If partial follow up data is available we will use this in analysis.

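### The primary outcome is set at both 6 weeks and 12 months and tested unadjusted at 0.05, and the plan does not say which contact decides

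*Combined protocol and SAP*

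**What the plan says.** All references are to the combined protocol and SAP.

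- **Outcome (2.2.1).** There is one primary outcome at two contacts: "Presence or absence of ganglion recurrence as reported by the patient at 6 weeks and 12 months". The primary objective in 2.1.1 carries no time point.
- **Test (10.2).** "The primary outcome will use chi-squared test (with or without continuity correction". The criterion is: "The difference between the two groups will be significant if the p values are less than 0.05". The section gives no deciding contact, order of testing, combined endpoint, both-required rule or adjustment.
- **Size (10.1).** "90 participants in each arm would give a 90% power to detect a change in recurrence rate of 25" percentage points. On the control rate: "We believe this is adequate as current recurrence rates are 59" per cent, with no time point. Two further scenarios give 62 per arm for 30 points and 46 per arm for 35 points.
- **Pointing to 12 months.** Section 1.2 argues that a year of follow-up is enough because most recurrences show within six months. Section 10.1 says that, after early closure, "all outstanding follow up will be completed and data included in final analysis".
- **Pointing to 6 weeks.** The early-closure looks in 10.1 are triggered when 51 and 69 participants have had the 6-week review, and they act on the recurrence difference.
- **Missing data (10.3).** "Any patients with missing all follow up data will be deemed to have not completed follow up". For the rest: "If partial follow up data is available we will use this in analysis".

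**The concern.** A primary outcome observed twice needs a rule that turns two results into one conclusion, and the plan has none. Three rules fit the wording: one contact decides, either contact suffices, or both are required. They have different error rates and different power. With no rule fixed, the choice could be made after the data are seen, and so could the choice of continuity correction. The sample size does not settle the matter, because its 59% belongs to no stated time point. The partial-data sentence in 10.3 adds to the ambiguity: a patient with only a 6-week report enters the analysis, but the plan does not say as what.

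**Working it through.** **1. Reproduce the planned numbers.** Inputs from 10.1 and 10.2: control rate p1 = 0.59, differences d of 0.25, 0.30 and 0.35, power 90%, alpha 0.05. Sidedness is not stated. Two-sided is inferred, because the one-sided formula gives 67 (uncorrected) or 75 (corrected) for the first scenario, not 90.

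Uncorrected: n = [1.960·√(2·p̄(1−p̄)) + 1.282·√(p1(1−p1)+p2(1−p2))]² / d².

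For d = 0.25: p2 = 0.34 and p̄ = 0.465, so n = [1.960·√0.49755 + 1.282·√0.4663]² / 0.0625 = 81.55, rounded up to 82.

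Corrected: n' = (n/4)·[1 + √(1 + 4/(n·d))]² = (81.55/4)·[1 + √1.1962]² = 89.4, rounded up to **90**.

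The same steps give 61.9 (**62**) and 45.1 (**46**) for the other two scenarios; uncorrected they give 56 and 40. All three planned figures therefore match a single two-sided 0.05 comparison with continuity correction.

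**2. False-positive rate under each rule.** Assumptions not in the documents: recurrence is cumulative (a recurrence at 6 weeks is also one by 12 months), the 59% applies by 12 months, and the 6-week rate is 10–50%. With n = 90 per arm and a and b recurrences, the statistic is χ² = 2n(|a−b|−c)² / [(a+b)(2n−a−b)], with c = 1 corrected and c = 0 uncorrected. It is rejected above 3.841. All joint 6-week and 12-month counts were enumerated exactly, with no true difference.

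| 6-week rate | Either contact, corrected | Either contact, uncorrected |
|---|---|---|
| 10% | 5.90% | 9.73% |
| 20% | 6.47% | 9.30% |
| 30% | 6.42% | 9.03% |
| 40% | 6.25% | 8.71% |
| 50% | 5.21% | 7.29% |

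12 months alone gives 3.63% corrected and 5.12% uncorrected.

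As a rough check, the correlation between the two tests is √[p6(1−0.59)/(0.59(1−p6))], where p6 is the 6-week rate. It runs from 0.28 to 0.83. The normal approximation then gives 9.5% down to 7.6%, in line with the uncorrected column.

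**3. Power.** For 59% v 34% at 12 months alone, exact power is 89.5% corrected and 92.0% uncorrected. If both contacts must be significant, power also depends on the 6-week effect, which the documents do not give. If PRP lowers both rates in the same proportion (34/59), joint power is below 90% at every 6-week rate examined. The best case is a 50% rate, with 78.6% corrected and 82.8% uncorrected, and power falls steeply at lower rates.

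**4. What the early-closure looks would see.** Under the same proportional effect, the 6-week difference is p6·(1 − 34/59) = p6·0.424. At p6 = 10% that is 4 points and at 50% it is 21 points, so a 25-point difference at 12 months appears as only about 4–21 points at 6 weeks.

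**The case against.** The strongest reply is that 12 months is the evident endpoint: section 1.2 justifies a year, and section 10.1 completes follow-up before the final analysis. That is a fair inference but not a designation. The only decision rule that the documents tie to a contact, early closure, uses 6 weeks.

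A second reply is that the inflation is small. With the continuity correction, the version that reproduces the sample size, either-contact success gives 5.2–6.5%. That stands. The larger figures need the uncorrected test, so part of the range comes from the open correction choice and not from the two contacts. The cumulative pattern is also assumed. Section 1.1 reports that many ganglia resolve spontaneously, so one present at 6 weeks could be gone by 12 months. That case was not calculated; it probably alters the size and not the direction.

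Three stronger readings are tempting and unsupported:

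- A reader might infer that the error rate is doubled. The 9.75% for two independent 0.05 tests ignores the correlation between contacts and the correction.
- A reader might infer a badly underpowered trial from the both-contacts rule. No section suggests that rule, and the loss largely reflects the assumed 6-week effect.
- A reader might infer that the sample size is wrong. It reproduces exactly for one comparison.

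**Conclusion.** The point holds. The plan names two contacts for one primary outcome, applies an unadjusted 0.05 criterion and never says which contact decides.

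Read at face value, as two primary tests each at 0.05 with success at either, the false-positive rate at 90 per arm exceeds the stated 5%: slightly with continuity correction and clearly without it. The size rests on the assumed cumulative outcome, 59% by 12 months and 10–50% by 6 weeks. It leaves out any effect of the early-closure looks, which are a separate multiplicity question. The omission itself rests on none of these assumptions.

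It needs settling before any comparative result is seen, which means before the first early-closure look.

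**What to change.** - **2.2.1 and 10.2:** name 12-month recurrence as the single primary endpoint, tested once in the final analysis at two-sided 0.05, with the continuity-correction choice fixed in advance. Make 6-week recurrence secondary.
- **10.1:** state that the 59% and the 25-, 30- and 35-point differences refer to that endpoint. Reconcile the early-closure looks with it, since they use 6-week data and thresholds taken from the same differences.
- **10.3:** state that a recurrence-free 6-week report does not stand in for a missing 12-month report.
- **Definition:** check the existing ganglion questionnaire, which was not among the supplied text, for whether 12-month recurrence means any recurrence since aspiration or a ganglion present at 12 months. It may already settle this.

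Counting 6-week recurrers who lack a 12-month report is optional, and at most a sensitivity analysis, because it can bias the comparison if loss differs between the unblinded arms. For example, take no true effect, 30% recurrence by 6 weeks, and 0% v 20% missing at 12 months. The second arm then reads (0.8·0.59 + 0.2·0.30)/(0.8 + 0.2·0.30) = 0.532/0.86 = 62% against 59%.

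**Cost.** A difference seen only at 6 weeks can no longer be the primary claim. The 90 evaluable and 100 recruited per arm stand if the 59% refers to 12 months. The 10% drop-out allowance must be checked against 12-month completion, because 10.3 treats only patients with no follow-up at all as lost. If 20% lacked a 12-month report (an assumption), 80 per arm would remain. Corrected power by the normal approximation would be Φ[(0.25 − 1/80 − 1.960·√(0.49755/80))/√(0.4663/80)] = Φ(1.09) = 86%, against 90% at 90 per arm.

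Keeping either-contact success with a 0.025 level at each contact would cost more. The corrected formula gives 105 evaluable per arm, and 105/0.9 is 117 recruited per arm, or 234 in total against the maximum of 200 in section 4.1.

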**2.2.2. Secondary Outcomes**

Patient reported outcome measure - PEM score which includes patient reported assessments of:

1. Stiffness
2. Pain
3. Cosmesis

### **3. STUDY DESIGN**

#### **3.1. Study Description**

##### **1. Patient selection**

All hand referrals vetted by [name] or Miss [name], those for dorsal wrist ganglia sent a letter of invitation and patient information. Patients responding to the letter with interested given an appointment at a special trial clinic.

Contact details will be provided to allow any issues to be clarified discussed before attendance at clinic if the patient desires.

##### **2. Assess eligibility/ enrolment in study – clinic visit 1**

- a) All patients assessed by the chief investigator [name] (DFML) or Miss [name] (KH).
- b) Clinical assessment of presence of ganglion.
- c) Ensure not meeting exclusion criteria.
- d) If eligible and willing to complete study commitments discuss study and answer questions.
- e) Once we are happy the patient has understanding of the study and its risks then the patient will be asked if they wish to enrol or if they would like more time to consider.
- f) If they are willing to participate they will then be offered treatment in the same visit or a return visit

##### **3. Intervention – clinic visit 1 or 2**

- a) Check understanding and continuing desire to participate in study if 2nd visit.
- b) Complete consent form.
- c) Patient fills out a PEM score and demographics collected on SOS.
- d) Randomisation.
- e) If in PRP group 15ml blood sample taken with Arthrex ACP double syringe and processed (see processing instructions in Appendix.9).
- f) Aspiration.
- g) If in PRP group - Injection of PRP (the same volume as aspirated).
- h) Pressure dressing with gauze, wool and crepe for 48 hours.

##### **4. Adverse event screening/ management**

Patients are offered two options at the treatment visit.

1. Routine review at 10 – 14 days at the clinic  
or
2. Telephone review at 7 days by Miss [name] who will have performed the procedure.

On telephone review if the patient is entirely happy that there are no concerns

then follow up will proceed by email or telephone as below.

If any concerns are raised, or if the patient desires, a face to face review will be arranged ideally within 24 hours but no longer than 72 hours. Recurrence or other outcomes will not be assessed at this time.

5. SOS/ Email/ Telephone interview - 1 (6 weeks)
  - a) Ganglion questionnaire
  - b) PEM score
  - c) Note any adverse events
  
6. SOS/ Email /Telephone interview - 2 (12 months)
  - a) Ganglion questionnaire
  - b) PEM score
  - c) Note any adverse events

### **3.2. Study Flowchart**

See Appendix 8.

## **4. STUDY POPULATION**

### **4.1. Number of Participants**

We would like to recruit a maximum of 100 patients who have a solitary dorsal wrist ganglion to each treatment arm. A total of 200 patients.

### **4.2. Inclusion Criteria**

Solitary dorsal wrist ganglion.

Over 16 years of age.

### **4.3. Exclusion Criteria**

Underlying wrist or ipsilateral arm pathology.

Unable to consent to treatment.

Unable or unwilling to attend follow up visits.

## **5. PARTICIPANT SELECTION AND ENROLMENT**

### **5.1. Identifying Participants**

[name] (DFML) or Miss [name] (CM) will vet all GP patient referrals for DWG. Each patient will be sent a letter of invitation and patient information. Patients will be asked to telephone DFML secretary for an appointment at a special trial clinic. At the clinic patients will have a history and examination performed to confirm the presence of the ganglion clinically and ensure no other pathology present. The study will be discussed, any questions answered and assess willingness to participate.

### **5.2. Consenting Participants**

To ensure that patients have adequate access to information and discussion prior to a potential 'one-stop' visit a letter will be sent to the patient prior to the clinic visit including the patient information. The patient information leaflet contains contact information allowing potential participants to contact a team member prior to attendance if they wish to clarify any issues or ask questions. On the day each patient will be seen by a member of the research team (Miss [name]) and eligibility assessed. If eligible the study will be discussed and a further opportunity to ask questions. Once we are happy the patient has understanding of the study and its risks then the patient will be asked if they wish to enrol or if they would like more time to consider. If they

are willing to participate they will then be offered intervention in the same visit or a return visit and they will be able to choose. Consent will be taken at the treatment visit if a second appointment is desired. If they are uncertain they will be provided with contact details and asked to call for an appointment if they decide they would like to participate in the future.

[name] (DFML) or Miss [name] (KH) will consent all patients prior to intervention being performed visit and record this on a written consent form (see attached documents). The form will be copied in triplicate for the patient, their medical notes and the trial file. All researchers taking consent have undergone Good Clinical Practice Training and are familiar with the procedure and its risks. The participants GP will be informed of the study with their consent.

**5.3. Screening for Eligibility**

Clinical screening for presence of ganglion.

**5.4. Ineligible and Non-Recruited Participants**

Ineligible and non-recruited patients will have only a standard GP clinic letter recorded. No other data will be taken or stored.

## **6. RANDOMISATION AND BLINDING**

### **6.1. Randomisation Details**

Once consent and understanding have been checked the patients will be allocated to one of the two groups randomly.

The study will be block randomized at a 1:1 ratio. We will create a block randomization scheme utilizing <http://www.randomization.com/>. All blocks will contain an increment of 10 subjects per group and there will be 20 blocks.

The randomization scheme will be enclosed in envelopes with each individual envelope containing one procedure per the block randomization process (see Section 3 for details on study groups). The exterior of the envelope will be marked with the study title and a number (1 through 200); however, the contents of the envelope will not be visible.

The randomization will be performed by Miss [name], who will also create the envelopes. Her only other role will be ensuring compliance with the follow up schedule.

For a particular subject, prior to the procedure, the investigator will select the next consecutive envelope and open the envelope to determine the procedure for the particular subject. Miss [name] is the contact point for randomization. The appropriate procedure will be performed, and the procedure along with the envelope number will be recorded in the study file.

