### **6.2. Blinding**

Blinding will not be performed to save the patients in aspiration alone group the unnecessary discomfort of blood sampling. We feel this is justifiable as the return of the ganglion or not is a physical finding and not influenced by other factors. The assessor and analyst will be blinded.

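### Section 6.1 fixes one block size (10 or 20, its figures conflict), so in this open single-site trial part of the allocation sequence can be deduced from earlier allocations

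*Combined protocol and SAP*

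**What the plan says.** Section 6.1 of the combined protocol and SAP states: "The study will be block randomized at a 1:1 ratio". It continues: "All blocks will contain an increment of 10 subjects per group and there will be 20 blocks". Nothing says that block sizes vary or that they are withheld from those who recruit. Envelopes are numbered 1 to 200, and before each procedure "the investigator will select the next consecutive envelope and open the envelope to determine the procedure for the particular subject". The procedure and the envelope number then go into the study file.

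The same section has real safeguards. Envelope contents cannot be seen, consent is checked before allocation, and the list and envelopes are made by someone of whom it says: "Her only other role will be ensuring compliance with the follow up schedule".

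The setting is described elsewhere:

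- Section 6.2: "Blinding will not be performed to save the patients in aspiration alone group the unnecessary discomfort of blood sampling". The assessor and the analyst are to be blinded.
- Section 7: one person performs all procedures.
- Section 10.4: there is a single site.
- Sections 3.1 and 5.2: a small clinical team judges eligibility and takes consent.
- Section 4.3: other disease of the wrist or of the arm on that side is an exclusion, found by history and examination (section 5.1).
- Section 5.4: patients who are ineligible or not recruited leave only a routine letter to the GP.

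**The concern.** With a fixed block size, the end of each block is determined by what came before it. In an open trial at one site the operator knows every earlier allocation, and consecutive envelope numbers show where blocks end once the size is known. The coming arm can then sometimes be worked out before a patient has been judged eligible or has agreed to take part.

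The decisions exposed to this are the judgement of whether the patient has other wrist or arm disease, and how enrolment is discussed. If either leaned on the coming arm, the groups could differ at baseline. The planned chi-squared test (section 10.2) makes no adjustment for that. The primary outcome is recurrence as the patient reports it (section 2.2.1), and the patient knows the arm, so concealment of allocation carries much of the protection of the comparison. With no data kept on patients who were not recruited, selective enrolment could not be checked afterwards.

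**Working it through.** **1. The plan's own figure.** Inputs from section 6.1: 20 blocks, 10 subjects per group, two groups, 200 envelopes.

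- As written: 20 × 10 × 2 = 400, not 200.
- Reading A, 10 subjects per block (5 per group): 20 × 10 = 200.
- Reading B, 20 per block (10 per group), with the number of blocks wrong: 10 × 20 = 200.

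The stated list cannot be reproduced. Both readings are carried forward.

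**2. Predictability.** Assume a person who knows every past allocation and the block boundaries. For a block of size 2m with m per arm:

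- expected allocations known with certainty = 2m/(m + 1);
- expected correct guesses, always naming the arm with more places left = m + (2^(2m)/C(2m, m) − 1)/2.

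Blocks of 10 (m = 5, 20 blocks):

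- certain: 10/6 = 1.67 per block; × 20 = 33 of 200 (16.7%), and never fewer than 20, because the last place in each block is always forced;
- correct guesses: 5 + (1024/252 − 1)/2 = 6.53 of 10 (65.3%, about 131 of 200).

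Blocks of 20 (m = 10, 10 blocks):

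- certain: 20/11 = 1.82 per block; × 10 = 18 of 200 (9.1%), and never fewer than 10;
- correct guesses: 10 + (1,048,576/184,756 − 1)/2 = 12.34 of 20 (61.7%, about 123 of 200).

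One list of 100 per arm (m = 100):

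- certain: 200/101 = 1.98 of 200 (1.0%);
- correct guesses: 100 + (17.75 − 1)/2 = 108.4 of 200 (54.2%).

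Chance alone gives 50%. Simulation of 100,000 blocks agreed with the formulas for blocks of 10 and 20.

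**3. Large blocks of undisclosed, varying size.** Sizes 10, 20 and 30 drawn at random (an assumed set), guessing from the running imbalance only: about 61% correct by simulation. Near-certainty goes because the boundaries are unknown, but guessing hardly improves on fixed blocks of 20.

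**4. What the single list costs at an early look.** The SD of the difference in arm sizes after n of 200 is sqrt(n(200 − n)/199). The efficiency lost from a difference D is (D/n)².

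- Section 10.1 takes its first look after 51 participants. If that means per arm, n = 102: SD = sqrt(102 × 98/199) = 7.1; 1.96 × 7.1 ≈ 14, i.e. 44 v 58; loss (14/102)² = 0.019, about 2%.
- If it means 51 in total: SD = sqrt(51 × 149/199) = 6.2; 1.96 × 6.2 ≈ 12. The difference must be odd, so 19 v 32. Loss (13/51)² = 0.065, or 0.056 with the unrounded 12.1; about 6%.

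**The case against.** The strongest reply is that concealment is already provided for: hidden contents, consecutive numbers, consent first, and a list maker with no stated recruiting role. That is fair, and the point should not be read as saying that the envelopes are insecure. These measures prevent reading the next envelope; they do not prevent inference from past ones.

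A second reply is that the contradictory block sentence leaves a reader of the protocol unsure where a block ends. That also stands in part: the percentages assume that the boundaries are known. But the sentence has to be corrected, and once it is, the protocol will state the size plainly. A pattern may also become visible as allocations build up.

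A third is that the usual remedy, small random blocks, is easier to guess. True, but it does not apply to a single long list, and the plan states no stratification that would call for tight blocks.

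Three stronger readings are tempting and not supported:

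- A reader might infer that staff could time treatment to suit the next envelope. Section 5.2 gives that choice to patients: "they will then be offered intervention in the same visit or a return visit and they will be able to choose".
- A reader might infer that the whole team sees every allocation. Only the operator is documented as doing so, and with names removed it cannot be confirmed how far operator, eligibility assessor and consent taker overlap.
- A reader might infer that the recurrence comparison is biased. Nothing in the documents shows that anyone tracked or acted on the sequence.

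**Conclusion.** The point holds as a design weakness that is cheap to remove. Section 6.1 must be reconciled in any case, and under either block size part of the sequence is deducible: about 17% certain and 65% guessable with blocks of 10, about 9% and 62% with blocks of 20.

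This rests on three assumptions: complete tracking of allocations, knowledge of the block boundaries, and a tracker who has some influence on eligibility or on the consent discussion. The figures are therefore ceilings on predictability. No step converts them into a shift in the recurrence difference, and the documents give no basis for one. Blinding the assessor and analyst does not alter this, since it acts after enrolment and the patient reports the outcome unblinded.

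**What to change.** 1. Replace the block sentence in section 6.1. Preferably use one permuted list of 200, 100 per arm. The alternative is large blocks of randomly varying size, accepting that guessing stays at about 61%.
2. Move any block details out of the protocol into a restricted document held by the existing list maker, so that the method stays documented. State outright that this person neither recruits nor treats.
3. Require the participant's study ID, date and time to be written on the sealed envelope before it is opened.

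The cost is a new list and envelopes and a short change to section 6.1, with no extra staff. The single list gives looser balance over calendar time, and at an early look it could lose the 2% (102 patients) or 6% (51 in total) of efficiency worked out above. Section 10.1 should say which of those two counts it means.
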